Specific Aim 2: To determine the effectiveness of LFR rTMS for the treatment of neuropsychiatric symptoms that are commonly seen as co-morbid phenomena in patients with post-TBI depression: (a) post traumatic stress disorder (PTSD) (b) sleep disturbance and (c) cognitive deficits. We hypothesize that LFR rTMS will be superior to sham treatment in reducing symptoms of PTSD, sleep disturbance and cognitive deficits, more specifically, memory, attention and executive function deficits. In addition, effectiveness of rTMS for the treatment of other behavioral symptoms (e.g. apathy, aggression) will be assessed.

Exploratory Analysis: A subset of subjects will be assessed using diffusion tensor imaging (DTI) to determine white matter integrity pre- and post-treatment in an effort to better understand neuro-anatomical correlates of NPS symptoms, symptom improvement, and the potential for LFR rTMS to influence white matter integrity.

Study Design: The study design will include a double-blind placebo-controlled trial of 30 TBI patients of mild & moderate severities. Subjects will be randomized to either active LFR rTMS (N=15) or sham treatment (N=15). All subjects will receive 20 LFR rTMS or sham treatments over 4 weeks, and will be followed thereafter for 3 months. Well-validated psychiatric instruments and cognitive assessments will be

used to compare the effectiveness of LFR rTMS versus sham treatment cross-sectionally at each of the visits and over time.

Relevance: If the proposed rTMS treatment is found to be efficacious, it can be transferred to clinical practice for soldiers with TBI-associated depression and other psychiatric symptoms. rTMS has minimal long-term side effects and is not known to negatively interact with pharmacotherapies. rTMS has the potential to have a broad impact on multiple areas of life functioning and, thus, has the potential to lead to improved instrumental life activities, employability, community re-integration and overall quality of life. Soldiers & civilians with increased emotional stability and improved cognitive skills can more effectively manage stress which, in turn, can dramatically reduce the likelihood of developing disorders associated with chronic stress.

2. Objectives

The overarching goal of this proposed proof of concept study is to determine the effectiveness of low frequency right (LFR) rTMS for the treatment of post-TBI depression and co-morbid psychiatric symptoms.

SPECIFIC AIMS & HYPOTHESES

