Aim 1: To determine the effectiveness of LFR rTMS for the treatment of: (a) post-TBI depression and (b) suicidal ideation. We hypothesize that LFR rTMS will be superior to sham treatment in: (a) reducing symptoms of depression and (b) reducing suicidal thoughts.

Aim 2: To determine the effectiveness of LFR rTMS for the treatment of neuropsychiatric symptoms that are commonly seen as co-morbid phenomena in patients with post-TBI depression: (a) post traumatic stress disorder (PTSD) (b) sleep disturbance and (c) cognitive deficits. We hypothesize that LFR rTMS will be superior to sham treatment in reducing symptoms of PTSD, sleep disturbance and cognitive deficits, more specifically, memory, attention and executive function deficits. In addition, effectiveness of rTMS for the treatment of other behavioral symptoms (e.g. apathy, aggression) will be assessed.

Exploratory Analysis: A subset of subjects will be assessed using diffusion tensor imaging (DTI) to determine white matter integrity pre- and post-treatment in an effort to better understand neuroanatomical correlates of NPS symptoms, symptom improvement, and the potential for rTMS to influence white matter integrity.

3. Background

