The pathophysiological consequences of trauma to the brain may be best conceptualized as the result of a combination of direct impact forces (i.e. at the site of impact) and acceleration-deceleration forces³⁶. The two most common sites of focal injury include the anterior and inferior frontal regions and the tips of the temporal lobes, as they sit on bony protuberances of the skull and are thus vulnerable to the impact forces³⁷. In addition to focal injury secondary to acceleration and deceleration forces, there are also backward/forward and rotational movements of the brain within the skull during TBI, resulting in diffuse axonal injury³⁸. Following acute TBI-induced physical injury, a cascade of metabolic events occurs, resulting in more damage. It is unclear how long neurotransmitter imbalances persist following TBI, as decreased levels of acetylcholine, serotonin and dopamine have all been noted, even in the chronic TBI period³⁹. Thus, the pathophysiology of TBI includes a combination of mechanical damage, metabolic disturbance, cytotoxic damage and neurotransmitter alterations which can persist for a prolonged period. In many patients, neuronal changes following TBI are subtle and cannot be identified by routine magnetic resonance imaging (MRI) or computerized tomography (CT) scans. However, Diffusion Tensor Imaging (DTI), which is known to be sensitive to the microscopic anatomical status of axonal structures, may have the potential to detect diffuse microstructural injury⁴⁰. DTI measures the microscopic random translational motion of water molecules⁴¹. Because freedom of motion is restricted by interactions with other molecules, the structure of axons, and integrity of neuronal membranes, DTI measures can be used as markers of tissue organization at a microscopic level. Therefore, DTI represents a promising approach to quantify microscopic brain damage by measuring both water diffusion (mean diffusivity; MD) and the degree of diffusion directionality, or anisotropy (fractional anisotropy; FA)⁴². In a pilot study to determine whether diffusion tensor imaging (DTI) measures of fractional anisotropy (FA) and mean diffusivity (MD), collected within 1 month of mild TBI (mTBI) could predict incident depression, Rao et al⁴³ noted a negative association between FA in the left superior and middle temporal gyri and severity of depression (indicating that decreased white matter integrity in these regions is associated with increased depression) and a positive correlation between MD and severity of depression in several fronto-temporal regions (indicating that increases in microstructural abnormalities in these regions are associated with increases depression). One goal of the current study is to determine whether these preliminary findings can be replicated. Because this is a treatment protocol, we also hope to characterize DTI changes associated with successful treatment of TBI depression and comorbid neuropsychiatric disturbances.

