The two groups will also be compared using similar statistical analyses of the NBRs-R scores. Additionally, a subset of subjects will also undergo MRI/DTI at baseline and at 3-month follow-up timepoint. DTI measures that will be used include fractional anisotropy (FA) and mean diffusivity (MD). The two groups will be compared on FA and MD values obtained at baseline and at 3-month follow-up using t-tests and linear regression analysis. Regions of interest will include frontal and temporal regions, fornix, cingulate, anterior limb of the internal capsule and genu and splenium corpus callosum.

Neuroimaging Analyses: As noted above, a subset of subjects will undergo MRI DTI scans pre- and post-LFR rTMS treatment. At the time of the initial screening, all subjects will be assessed for MRI safety using the questionnaire below. A positive answer to any one of the question will exclude them from having MRI. Also, only subjects who definitively agree to have brain MRI will have the scan.

MRI Questionnaire

Please reply yes or no to the following questions.

Do you have the following?:

Brain aneurysm clips

Any type of artificial heart valve

A heart defibrillator or pacemaker

Inner ear (cochlear) implants

Recently placed artificial joints

Any type of vascular stent
Any metal pieces in your body or eyes

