DTI data will be acquired with a single-shot, echo-planar imaging (EPI) sequence with sensitivity encoding (SENSE), using a parallel-imaging factor of 2.5. The imaging matrix is 96 X 96 with a field-of-view of 212 X 212 mm (nominal resolution, 2.2 mm), zero-filled to 256 X 256 pixels. Transverse sections of 2.2 mm thickness will be acquired parallel to the anterior commissure-posterior commissure line. A total of 60-65 sections will cover the entire hemisphere and brainstem without gaps. Diffusion-weighted images at $b = 700$ s/mm² along 32 directions will be acquired in addition to five additional images with minimal diffusion weighting ($b \approx 33$ mm²/sec). The scanning time per dataset will be approximately 4 minutes. To enhance the signal-to-noise ratio, this procedure will be repeated 3 times. From this, fractional anisotropy (FA) and mean diffusivity (MD), and eigenvalues will be calculated. In this proposal, we will perform hypothesis-based regional analysis of the DTI-derived parameters using manual regions of interest (ROI). ROI will include frontal and temporal regions, the fornix, cingulate, anterior limb of the internal capsule, genu and splenium corpus callosum. We will also perform whole-brain analyses using a brain normalization technique developed in [name] lab¹⁰⁸. Combination of the two approaches (manual regional and automated whole brain analyses) will ensure the robustness and regional specificity of the ROI-based findings.

Other Scales: Other scales described below will be used to assess medical comorbidity, pain, fatigue and postconcussive symptoms all of which can confound the results and will be controlled in the different regression analyses.

Medical Co-morbidity: The General Medical Health Rating (GMHR)¹⁰⁹ will be used to assess overall medical co-morbidity. The scale is simple to use and provides a rating of overall general medical health taking into consideration all medical problems and medications. The scores on this scale ranges from 1 (poor; unstable medical health) to 4 (stable; excellent health). The PI has used this scale previously in her TBI studies.

Pain: The SF-36 bodily pain scale¹¹⁰ will be used to assess pain. It has been found to be a valid measure of pain assessment.

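### No DTI analysis is stated to use the baseline scan as a covariate; naming it in the planned regression would sharpen the exploratory comparison at almost no cost

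*Combined protocol and SAP*

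**What the plan says.** The imaging question appears in three places. The Abstract and the Objectives (section 2) say that a subset will have diffusion tensor imaging "to determine white matter integrity pre- and post-treatment", partly to learn about "the potential for rTMS to influence white matter integrity". The Background, at the end of the part on pathophysiology, adds: "we also hope to characterize DTI changes associated with successful treatment of TBI depression".

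The scans are planned in section 6, Exploratory Analyses: "a subset of subjects will also undergo MRI/DTI at baseline and at 3-month follow-up timepoint". The payment section (section 8) budgets for twenty-five subjects to be paid for both a pre-treatment and a post-treatment scan.

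The between-arm analysis is one sentence in section 6, which compares the arms on FA and MD "values obtained at baseline and at 3-month follow-up using t-tests and linear regression analysis". The regression's outcome, treatment term and covariates are not given. The later text on neuroimaging covers acquisition, regions of interest and whole-brain analysis, and adds no between-arm model.

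Two neighbouring statements bear on how that sentence is read. Under Other Scales, medical comorbidity, pain, fatigue and postconcussive symptoms are described as variables "all of which can confound the results and will be controlled in the different regression analyses"; baseline FA and MD are not on that list. For the secondary outcomes, including polysomnography and cognition (each also measured twice), the plan uses random effects models with a time-by-treatment term. The NBRs-R gets similar analyses. DTI is then given its own methods, and that longitudinal model is not extended to it.

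**The concern.** Whether the treatment influences white matter is a between-arm question about the follow-up scan, and each subject's own pre-treatment scan is an obvious candidate to explain part of the variation in it. The plan collects that scan but does not say that any analysis will use it as a covariate. Someone following the text could report a t-test on each occasion plus a regression without the baseline value, and would have complied.

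Two things are then at stake. The first is precision: with some 25 subjects, an unadjusted comparison detects only very large differences. The second is interpretability: a chance gap between small arms at baseline carries partly into the follow-up comparison. The baseline t-test remedies neither. In a randomized trial it can only show whether chance produced a gap, and it says nothing about what the treatment did.

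**Working it through.** **What there is to reproduce.** The documents give no sample size justification, power, SD, effect size or scan-to-scan correlation for DTI. Table 7 sizes the trial on HAMD remission and is not affected.

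**Inputs.**
- 25 scanned subjects (section 8). The arm split is not stated; with 1:1 randomization I assume 13 and 12, all with both scans.
- Two-sided 0.05 (section 6, General Description).
- r, the correlation between baseline and follow-up FA or MD, is not in the documents; the assumed range is 0.3 to 0.9.
- Equal SDs at the two scans (assumed). Differences are in SD units.

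**Precision.** Relative to a follow-up-only t-test, adjusting for the baseline value multiplies the variance by 1 − r², so the standard error ratio is √(1 − r²). Estimating the baseline slope costs a variance factor of about 1 + 1/22, which is √(23/22) = 1.022, or 2%, on the standard error. Minimum detectable differences at 80% power, and power for an assumed 0.8 SD difference, come from the noncentral t distribution (23 df unadjusted, 22 df adjusted) and include that factor.

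| Analysis | SE ratio √(1 − r²) | Detectable at 80% power (SD) | Power at 0.8 SD |
|---|---|---|---|
| Follow-up t-test | 1 | 1.17 | 48% |
| Adjusted, r = 0.3 | 0.95 | 1.14 | 50% |
| Adjusted, r = 0.5 | 0.87 | 1.04 | 58% |
| Adjusted, r = 0.7 | 0.71 | 0.86 | 74% |
| Adjusted, r = 0.8 | 0.60 | 0.72 | 88% |
| Adjusted, r = 0.9 | 0.44 | 0.52 | 99% |

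Expressed as sample size before the small-sample factor, r = 0.7 gives 25 / (1 − 0.49) = 25 / 0.51 = 49 subjects' worth of information.

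The table leaves out the stratum term. If stratum were unrelated to FA, two covariates would bring the variance penalty to about 22/20 = 1.10 with 21 df. The detectable difference would then be about 1.18 SD at r = 0.3 (no gain over 1.17) and 0.88 SD at r = 0.7 (still a clear gain).

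**Change score as an alternative.** Its variance factor is 2(1 − r): 1.4 at r = 0.3, 1.0 at r = 0.5 and 0.6 at r = 0.7. It is worse than ignoring baseline below r = 0.5, and its factor is never smaller than 1 − r². With r unknown, baseline adjustment is the safer choice.

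**Chance imbalance.** The baseline arm difference has standard error √(1/13 + 1/12) = 0.40 SD. A gap beyond 0.5 SD in either direction lies 0.5 / 0.40 = 1.25 standard errors out, which has probability of about 0.21. A fraction r of any gap is expected to reappear at follow-up: 0.8 × 0.5 = 0.40 SD at r = 0.8, as large as the unadjusted standard error.

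**Validity.** In 4,000 simulated trials per setting at r = 0.5, 0.7, 0.8 and 0.9, the follow-up t-test, the adjusted regression and the change-score test all rejected a true null in 4.2% to 5.6% of trials.

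**The case against.** The best defence is that the plan already names linear regression, which is the tool recommended here, and does not exclude the baseline scan from it. That stands. A reader might infer that the investigators chose t-tests in place of baseline adjustment; the text shows no such choice, only a regression whose terms are left open. The confounder list under Other Scales is not said to be complete either, so the absence of baseline FA and MD from it is silence and not a refusal.

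A reader might also infer that the planned comparison does not test the stated question. It does. Under randomization, and provided the scanned subset is formed independently of assignment, the follow-up difference between arms is an unbiased estimate of the treatment's influence on white matter, and the simulated error rates confirm that the test is sound. Chance baseline gaps are already allowed for in the 5% error rate; adjustment helps in interpreting the one trial actually run.

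Nor do the documents support saying that stable differences between people would drown any effect. They give no SD, effect size or repeat-scan correlation, and at r = 0.3 the gain is negligible.

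It could also be said that baseline FA would enter if its t-test were significant, since the random effects models adjust for baseline variables that differ significantly. That rule is not extended to DTI. Even if borrowed, it would act only on a gap of about 2.07 × 0.40 = 0.83 SD or more (t critical value on 23 df), leaving smaller gaps unadjusted and forgoing the precision in most trials.

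What remains is that a better analysis of data already being collected is available, and the plan does not commit to it.

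**Conclusion.** The point holds as a free improvement of low severity. The DTI sentence leaves the regression open, and no stated DTI analysis takes the baseline scan as a covariate. The follow-up t-test is valid but inefficient, and the baseline t-test does not bear on treatment effect.

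The size of the loss cannot be fixed from the documents. Over the assumed range of r, adjustment lowers the standard error by about 5% at r = 0.3, 29% at r = 0.7 and 56% at r = 0.9, less a few percent for small numbers. These figures rest on 25 subjects split 13 and 12, both scans obtained, and equal SDs. The analysis is exploratory in a pilot of 30, so the primary and secondary conclusions and Table 7 are unaffected.

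**What to change.** Replace the DTI sentence in section 6 with a stated model. For each prespecified region, regress FA at the 3-month follow-up scan (taken here as the week 16 visit) on arm, baseline FA in that region and the time-since-injury stratum used in the randomization (under 5 years, or 5 years and over); do the same for MD. Report the adjusted arm difference with its 95% interval for every region, labelled exploratory. Show baseline FA and MD by arm descriptively, so that any imbalance stays visible, and drop the baseline significance test.

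The cost is one or two sentences and no new data. Statistically, it is the small-sample penalty shown above: if r turns out near 0.3 and the stratum explains nothing, the model is about level with the t-test. If r is 0.5 or more, it is better.

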Study Design: We propose a double-blind placebo controlled proof of concept pilot study of active versus sham LFR rTMS for the treatment of TBI depression. As noted above, all subjects will be screened prior to randomization. During the screening visit, all subjects will undergo a complete psychiatric evaluation as well as formal cognitive testing. In addition, if there is any possibility of pregnancy or unstable medical status, the PI or physician co-investigator will ask the potential subject's treating psychiatrist or primary care physician (PCP) to conduct a urine pregnancy test and/or bloodwork to rule out infections and liver, kidney or thyroid abnormalities. If the potential participant does not have a PCP or psychiatrist, a lab requisition will be provided to the participant. He/she will be considered for the study only after the lab results are reviewed by the study physician and found to be normal. .

Subjects will be randomized using a custom in-house software method, and will be stratified on time since injury: <5 years post injury versus ≥ 5 years.

All members of the research team will be blind to individual subjects' treatment condition, with the exception of the rTMS staff member, [name]. The success of subject blinding will be evaluated by asking subjects, during the first and last week of treatment, whether they believe that they received active or sham rTMS treatment. The rTMS technician will ask this question and note down the answer in the weekly assessment form.

Study Treatment: Subjects will receive either LFR rTMS or sham treatment.

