An Adverse Events questionnaire will be used to record study side-effects. This questionnaire will capture the date, visit number, adverse event description, event start date, event end date, relationship to the device, severity, whether it is a SAE (Serious Adverse Event), action taken and outcome, The PI and/or, Medical Monitor and clinical co-investigators will make decisions regarding the severity of the side-effects, the relationship to the device and whether or not it a SAE.

Early stopping rules:

Subjects will be removed from the study early if it becomes clear that the risks of continuing treatment outweigh the benefits of continuing the study. In this research study, there is no alternative treatment other than treatment with LFR rTMS vs sham. If subjects are unable to complete the study, they will be either be absorbed in the PI's Brain Injury clinic or referred to appropriate treatment centers, if they so desire.

The following will be used to define unacceptable tolerability:

This decision will be made by a review committee chaired by the Medical Monitor.

- (a) Clinically judged treatment-related death in one research participant. Clinically judged medication related death in one research participant. If a death occurs the case will be reviewed to decide if the death was medication related. The review committee will include [name] (PI), and members of the Data & Safety monitoring board: [name], [name] and [name]. All members of the DSM board are psychiatrists and faculty Johns Hopkins University. The 3 DSM members are not connected with the study.

[name] will also serve as the medical monitor. He is currently involved in several clinical trials and therefore, is well-suited for this role. As the medical monitor, his job will be to: (a) review and provide appropriate recommendations to address unanticipated problems that may arise during the study, and

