(b) if anything adverse happens during the study period, he will provide an unbiased written report to the Johns Hopkins IRB and Department of Defense Human Research Protection Office (DoD HRPO) within 10 days of the event. He will not work under the supervision of the PI or any other research staff but will be available to the PI and research team to address any issues that arise during the study period. He will have the authority to stop the study, remove subjects from the study and take whatever steps are necessary to protect the safety and well-being of research volunteers until the IRB can assess the medical monitors report.

(a) Clinically judged treatment related hospitalization and/or emergency room visit in 20 % or more participants.

(b) Drop out of the study secondary to intolerable side-effects in 30% or more of participants
If any of the above happens, the study will be immediately terminated.

If either of the above happens, the study will be immediately terminated.

Otherwise, the Adverse-Events Protocol will be used to track the nature, visit time, and severity of side-effects

The PI and her research team will meet regularly to discuss the progress of the study.

In summary, all unanticipated problems involving risk to subjects or others related to participation in the study will be promptly reported both to Hopkins IRB and to the USAMRMC, Office of Research Protections, Human Research Protection Office (<[contact]>; email - [contact] or by [contact]).

A complete written report will follow the initial notification. In addition to the methods above, the complete report will also be sent to the U.S. Army Medical Research and Materiel Command, ATTN: MCMR-ZB-PH, [name].”

7. Risks & Benefit

As with any medical treatment, rTMS carries a risk of side effects. However, rTMS is generally well-tolerated and only a small percentage of patients discontinue treatment because of side effects which are even less frequent with LFR than with HFL rTMS.

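### The PI sits on the committee that judges whether a death is treatment related, with no provision for abstaining or leaving

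*Combined protocol and SAP*

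**What the plan says.** The relevant text is in section 6, under Early stopping rules and the adverse-event paragraph just before it.

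- **Who decides.** On unacceptable tolerability: "This decision will be made by a review committee chaired by the Medical Monitor".
- **Who sits.** "The review committee will include [name] (PI), and members of the Data & Safety monitoring board". The board has three members, described as faculty psychiatrists without a connection to the study.
- **What is decided.** "If a death occurs the case will be reviewed to decide if the death was medication related".
- **Criteria that need a judgement of cause.** "Clinically judged treatment-related death in one research participant", and "Clinically judged treatment related hospitalization and/or emergency room visit in 20 % or more participants". A third criterion concerns drop-out for intolerable side effects in at least 30% of participants.
- **Consequence.** "If any of the above happens, the study will be immediately terminated".
- **Event-level attribution.** The adverse-event paragraph lets the PI and/or the medical monitor and clinical co-investigators decide severity, relationship to the device and seriousness.
- **The monitor.** "He will not work under the supervision of the PI or any other research staff". He may stop the study or remove participants until the IRB can assess his report. He also reports adverse happenings in writing to the Johns Hopkins IRB and the DoD human research protection office within 10 days.

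The section gives no voting rule, quorum or recusal rule, and does not say that the PI attends without a vote.

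**The concern.** A study-level stopping rule that turns on clinical attribution is only as sound as the people who make the attribution. The PI designed the trial, runs it and has an ordinary professional interest in seeing it finished. No particular conflict is documented, and none is needed for the point: this is the usual reason for keeping investigators out of stopping decisions.

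The plan seems to accept that reasoning. It goes out of its way to say that the board members are outside the study and that the monitor does not answer to the PI. It then seats the PI with them at the one decision for which that distance matters most. What is at stake is a possible bias towards finding an event unrelated, and the credibility of such a finding to the IRB and the funder even if no bias occurred.

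**Working it through.** The plan has no figure to reproduce here; the check is a reading of the provisions against one another, with a small count at the end.

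**1. Does the attribution decide termination?** One death meets the first criterion, and a met criterion ends the study at once. There is no separate vote to terminate. The only discretion lies in whether the death counts as related, so that judgement settles the outcome under this criterion.

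**2. Is the PI's part in it stated or merely left open?** Stated. The PI is listed as a member. Nothing elsewhere in the protocol turns that membership into an advisory role.

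**3. Does the point reach beyond deaths?** Yes, on a plain reading. The sentence naming the committee as decision-maker introduces the whole definition of unacceptable tolerability, although the membership sentence appears under the death criterion. The hospitalization and emergency-visit criterion also needs a judgement of relatedness, and the PI may already have supplied it for each event. Section 4 further makes the PI responsible for psychiatric admission when outpatient care is not appropriate. The same person may thus admit the participant, judge the cause, and sit on the body that decides whether the threshold is reached.

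**4. How much can one classification matter?**
- Death criterion: the threshold is 1, so one classification is decisive.
- 20% criterion: the plan does not state the denominator. If it is all 30 planned participants, the threshold is 0.20 × 30 = 6, and 5/30 = 16.7% falls short. If it were counted with, say, 10 enrolled (an assumption), the threshold would be 0.20 × 10 = 2. At the margin a single classification decides this criterion too.

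**5. Could the PI's vote be pivotal?** This needs three assumptions that the plan does not state: the PI votes, a simple majority decides, and the chair has no casting vote.
- If the monitor is one of the three board members, as the text suggests, the committee has 3 + 1 = 4 members. Independent votes of 3–0 leave the PI without influence (3–1 at worst). A 2–1 split for related becomes 2–2 if the PI dissents.
- If the monitor is a further independent person, the committee has 4 + 1 = 5 members, and the PI decides only a 2–2 split (3–2).

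These counts illustrate what could happen. They are not properties of the plan; a casting vote for the monitor, for instance, would remove the four-member tie.

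**The case against.** The strongest reply is that the plan already contains the safeguard. The monitor chairs the committee, is outside the PI's supervision, may halt the trial without anyone's agreement, and reports to two outside bodies. The PI is one member among independent colleagues and contributes first-hand clinical knowledge. Other protections also exist: side effects are checked at each treatment and office visit, and individual participants can be withdrawn.

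Most of this stands, and it rules out several stronger readings that a reader might infer.

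- *The PI could keep the study open against safety advice.* Not supported. The PI cannot prevent the monitor from stopping the study.
- *The committee votes on terminating the PI's own trial.* Not as written. It judges whether a criterion is met; termination then follows automatically.
- *The plan contradicts its own claim of independence.* Not quite. Independence is asserted for the board members and the monitor, never for the review committee.
- *PI membership forces a choice between unblinding the PI and judging without arm information.* Section 4, Study Design, says "All members of the research team will be blind to individual" subjects' assignment, apart from one rTMS staff member. Nothing says that the committee receives arm information or needs it, and relatedness can be judged blind. The dilemma rests on a disclosure step that the plan does not contain.

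What the reply does not answer is why the PI should take part in the judgement. The monitor's own power is an interim one, running until the IRB assesses his report, whereas the protocol's defined criteria go to the committee. Clinical knowledge can be supplied without a vote.

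**Conclusion.** The concern holds in a limited form. A listed member with an interest in continuation takes part in the attribution that, for a death, determines whether the trial ends, and may also have judged individual events that feed the 20% criterion. That weakens a separation which the plan otherwise builds with care.

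The size is modest and cannot be given as a probability. The independent chair, his own stopping authority and the outside reporting cap the harm, and the efficacy analysis is unaffected. The conclusion rests on two readings: that listed membership implies participation in the decision, since nothing says otherwise, and that the same committee handles all the tolerability criteria. It does not depend on the vote counts. The change should be made because it removes an avoidable source of bias from a safety decision at almost no cost.

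**What to change.** In section 6, Early stopping rules, add one or two sentences to this effect: the PI presents the case and answers the committee's questions, then takes no part in deliberation or voting; the medical monitor and the board members alone decide relatedness and whether a stopping criterion has been met, including the hospitalization and emergency-visit criterion. A short statement of the quorum and of how ties are resolved would complete it.

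While that paragraph is open, reconcile its two descriptions of the death criterion, which refers in one place to treatment and in another to medication, although the intervention is a device.

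No additional people, visits or data are required, because the monitor and board are already appointed. No threshold changes, and no procedure for releasing arm information is needed. The one small downside is that the PI's knowledge of the participant reaches the committee only through the presentation and the answers to questions.
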